6.3.1.3 Assessment of Severity

Whenever possible, the intensity of clinical AEs will be graded according to National Cancer Institute (NCI) CTCAE (Version 5.0 or any latest version) grading system. Adverse events not listed in the NCI CTCAE grading system will be graded on a 5-point scale (mild, moderate, severe, life-threatening, and death) as described below, and reported in detail as indicated on the eCRF.

Severity Grading for Adverse Events Listed in NCI CTCAE (Version 5.0 or any Latest Version):

- **Grade 1: Mild:** asymptomatic or mild symptoms; clinical or diagnostic observations only; intervention not indicated.
- **Grade 2: Moderate:** minimal, local, or noninvasive intervention indicated; limiting age appropriate instrumental activities of daily living (ADL) (Instrumental ADL refers to preparing meals, shopping for groceries or clothes, using the telephone, managing money, etc).
- **Grade 3: Severe:** or medically significant but not immediately life-threatening; hospitalization or prolongation of hospitalization indicated; disabling; limiting self-care ADL (Self-care ADL refers to bathing, dressing and undressing, feeding self, using the toilet, taking medications, and not bedridden).
- **Grade 4: Life-threatening:** life-threatening consequence; urgent intervention indicated.
- **Grade 5:** death related to AE.

Note the distinction between the severity and the seriousness of an AE. A severe event is not necessarily an SAE. For example, a headache may be severe (interferes significantly with subject's usual function) but would not be classified as serious unless it meets 1 of the criteria for SAEs, listed in [Section 6.3.1.1.1](#).

6.3.1.4 Assessment of Causality

The investigator is obligated to assess the relationship between study intervention and each occurrence of AE/SAE. The investigator will use clinical judgment to determine the relationship. Alternative causes, such as underlying disease(s), concomitant therapy, and other risk factors, as well as the temporal relationship of the event to study intervention administration will be considered and investigated. The investigator will also consult the IB and/or product information, for marketed products, in his/her assessment. There may be situations in which an SAE has occurred, and the investigator has minimal information to include in the initial report in the eCRF. **However, it is very important that the investigator always make an assessment of causality for every event before the initial transmission of the SAE data via eCRF.** The investigator may change his/her opinion of causality in light of follow-up information and change the assessment in the eCRF, which will trigger an alert to the sponsor's designated safety services. The causality assessment is 1 of the criteria used when determining regulatory reporting requirements.

The following “binary” decision choice will be used by the investigator to describe the causality assessment:

- Reasonable possibility of relatedness (i.e., related)
- No reasonable possibility of relatedness (i.e., not related)

The term “reasonable possibility of relatedness” is meant to convey, in general, that there is enough evidence or argument to suggest the causal relationship. The investigator should consider the following before reaching a decision on causality assessment:

- Time relationship between study treatment intake and event's onset;
- Dechallenge;
- Rechallenge;
- Medical history;
- Study treatment;
- Mechanism of action of study treatment;
- Class effect;

- Concomitant treatments in use;
- Withdrawal of study treatment;
- Lack of efficacy/worsening of existing condition;
- Erroneous treatment with study medication or concomitant medication;
- Protocol-related process.

Action taken with study treatment due to the AE:

- Dose not changed;
- Drug interruption;
- Drug withdrawn;
- Unknown;
- Not applicable.

Outcome:

Each single AE must be rated by choosing 1 of the following:

- Recovered/resolved;
- Recovering/resolving;
- Not recovered/not resolved;
- Recovered with sequelae/resolved with sequelae;
- Fatal;
- Unknown.

Note: If an event is stabilized per opinion of the investigator, then outcome option of "Not recovered/not resolved" to be selected in drop down list of outcome in eCRF. However, in AE/SAE description free filed of eCRF, investigator has to mention the event is assessed as "Stabilized" on a given date.

The investigator and the sponsor (or sponsor's designee) will review each SAE report and the sponsor/CRO will evaluate the seriousness and the causal relationship of the event to study intervention. In addition, the sponsor (or sponsor's designated agent) will evaluate the

expectedness according to the reference document (IB or SmPC or PI). Based on the investigator and sponsor's assessment of the event, a decision will be made concerning the need for further action.

6.3.1.5 Reporting of Serious Adverse Events

Investigators and other site personnel must inform as appropriate to the sponsor's designated safety services of any SAEs that occur (whether or not attributable to the study treatment) in the course of the study within 1 day (24 hours) (i.e., immediately but no later than the end of the next calendar day) of when he or she becomes aware of it.

Follow-up information on SAEs must also be reported by the investigator to the sponsor's designated safety services within the same time frames.

If a nonserious AE becomes serious, this and other relevant follow-up information must also be provided to sponsor's designated safety services within 24 hours as described above.

All SAEs must be reported, whether or not considered causally related to the study treatment or study procedure(s). All SAEs will be recorded in the eCRF; paper forms will be used as a back-up only if the eCRF is unavailable. The investigator is responsible for informing the IEC/IRB of the SAE per local requirements.

Source documents relevant for the SAE must be reported upon request by sponsor's designated safety services. Due to data protection laws, please ensure redaction of the subject's identifiers (name, address, and date of birth [only year of birth is allowed]) from the discharge summary, autopsy report, laboratory reports, and any other documents/reports when sending to the sponsor's designated safety services.

The completed and signed SAE or pregnancy report form must be attached to the email. A notification email of the event describing it in the email text is not sufficient.

There may be situations when an SAE has occurred, and the investigator has minimal information to include in the initial SAE report. However, it is very important that the investigator always makes an assessment of causality for every event prior to transmission of the SAE report form. Minimum criteria are identifiable subject (number), a suspect product (i.e., study treatment or concomitant medication), an identifiable reporting source (investigator/study site identification), and an event or outcome that can be identified as

serious. The investigator may change his/her opinion of causality in the light of follow-up information, amending the SAE report form accordingly. The causality assessment is 1 of the criteria used when determining regulatory reporting requirements for SAEs.

When an SAE is discovered by the site or is identified by a clinical research associate during site visits, SAEs will be entered by the site members into the eCRF, which contains specific questions for events regarded as serious. The designated personnel will receive the alert through automated email notification.

The sponsor/designee representative will work with the investigator to compile all the necessary information and ensure that the appropriate sponsor representative receives a report within 1 calendar day (24 hours) for all fatal and life-threatening cases and within 5 calendar days for all other SAEs per the applicable local regulatory guidelines. All SAEs and follow-up information on the SAEs are to be reported to **CI** Pharmacovigilance in 24 hours regardless of seriousness criteria.

Prompt notification of SAEs to the sponsor/designee, as described above, is essential so that regulatory requirements and ethical obligations to the subjects involved in the study can be met. The investigator is responsible for informing the IEC/IRB of the SAE per local requirements. Unblinding relating to suspected unexpected serious adverse reactions (SUSARs) (if required) will be performed by the sponsor/designee in accordance with standard operating procedures (SOPs), working practice documents, and documented study-specific procedures.

6.3.1.6 Suspected Unexpected Serious Adverse Reactions

Any AE that is serious, associated with the use of the study intervention, and unexpected (SUSAR) has additional reporting requirements as described below.

- If the SUSAR is fatal or life-threatening, associated with study intervention, and unexpected, regulatory authorities and IEC/IRB will be notified within 7 calendar days after the sponsor learns of the event. Additional follow-up (cause of death, autopsy report, and hospital report) information should be reported within an additional 8 days (15 days total).

- If the SUSAR is not fatal or life-threatening but is otherwise serious, associated with study intervention, and unexpected, regulatory authorities and IEC/IRB will be notified within 15 calendar days after the sponsor learns of the event.

The sponsor's designated safety services will also provide periodic and annual safety updates to the regulatory authorities, IEC/IRB responsible for the study, and investigators per local regulations. These updates will include information on SUSARs and other relevant safety findings.

6.3.2 Abnormal Laboratory Values/Vital Signs Measurements/Electrocardiograms

Laboratory/vital signs/ECG abnormalities should be reported as an AE/SAE if any 1 of the following criteria is met:

- Result is associated with signs/symptoms;
- Requires additional diagnostic testing and/or interventions;
- Leads to a change in dose, discontinuation of, or interruption to the study treatment.

Repeats of an abnormal test result without any of the above criteria do not constitute an AE.

Any test result determined to be an error is not required to be reported as an AE.

6.3.3 Deaths

Should a death occur within the study period, an AE form and an SAE report form should be completed, detailing the AE that resulted in the death (Note: death is an outcome, not an event). The SAE must be reported to the sponsor or the sponsor's designated safety services within 24 hours as described in [Section 6.3.1.5](#).

Expedited reporting is determined by the CRO depending on the information provided by the site, e.g., AEs that are fatal/life-threatening and related to the study drug would be considered as expedited and reported to regulatory authorities and IEC/IRB within 7 calendar days. Adverse events with any other seriousness criteria and relatedness would be reported to regulatory authorities and IEC/IRB within 15 calendar days.

6.3.4 Clinical Laboratory Assessments

Clinical laboratory assessments will be performed as indicated in [Table 14-1](#). Hematology, biochemistry, and urinalysis will be conducted at the following visits: screening, on Day 1, Day 15, and at Weeks 4, 8, 12 (EOS/ET), and 26 (additional follow-up). Serum pregnancy test will be conducted at screening, Week 12 (EOS/ET), and Week 26 (additional follow-up) visits. Urine pregnancy test will be conducted on Day 1 prior to randomization, and Day 15 (before dosing), at Week 4 and Week 8 visits.

Hematology, biochemistry, urinalysis, and pregnancy tests will be performed by the local laboratory according to local practice. Local laboratory normal ranges will be collected prior to first subject first visit at each site and provided to data management via the study team. Laboratory results collected from the local laboratory should be entered in the eCRF by the investigator. The following parameters will be assessed:

- Hematology: red blood cell count, white blood cell count with differential count and percentages (including absolute neutrophil count), total hemoglobin, hematocrit, platelet count, and prothrombin time.
- Biochemistry: creatinine, blood urea nitrogen, fasting serum glucose, aspartate aminotransferase, alanine aminotransferase, gamma-glutamyl transpeptidase, total bilirubin, albumin, chloride, calcium, phosphorous, uric acid, total protein, sodium, and potassium.
- Serum IgG and IgM.
- Urinalysis (specific gravity, pH, protein, glucose, and blood).
- Pregnancy test: serum β -hCG test and urine pregnancy test for WOCBP.
- Serum FSH for postmenopausal women.

Note: Per CTFG 2014 guidelines, a postmenopausal state is defined as no menses for 12 months without an alternative medical cause. A high FSH level in postmenopausal women is to be used to confirm a postmenopausal state in women not using hormonal contraception or hormonal replacement therapy. However, in the absence of 12 months of amenorrhea, a single FSH measurement is insufficient. Hence, in such cases or in some other cases in which if menopausal status is difficult to confirm, then investigators are advised to investigate further to rule out childbearing potential along with serum FSH.

Blood and urine collection and blood sample preparation will be performed according to procedures from the local laboratories.

6.3.5 Physical Examination

Complete physical examinations will be performed as indicated in [Table 14-1](#). The following parameters and body systems will be examined and any abnormalities described: weight, height (at screening visit only), general appearance, skin (e.g., presence of rash), head, eyes, ears, nose, throat, lungs (auscultation), heart (auscultation for presence of murmurs, gallops, rubs), extremity exam for the presence of peripheral edema, abdominal (palpation and auscultation), and neurologic (mental status and motor and sensory function). The physical examination must include a thorough assessment of the lymph nodes, liver, and spleen. The genitourinary system may be excluded unless there are signs or symptoms involving that system. Any clinically significant changes from the screening visit after initial dosing with study treatment should be recorded as AEs.

6.3.6 Vital Sign Measurements

Vital signs, including heart rate, seated BP, respiration rate, and oral body temperature, will be measured as detailed in [Table 14-1](#) and in the event of an IRR.

Blood pressure will be measured in the subject's arm and recorded to the nearest mmHg after the subject has been seated quietly for at least 2 minutes. The same arm and position should be used throughout the study, using an appropriate cuff size. All BP readings should be measured after resting for at least 5 minutes. When the timing of these measurements coincides with blood collection, the BP and heart rate should be obtained first.

Vital signs are to be obtained prior to each study treatment infusion, every 30 minutes (\pm 5 minutes) during infusion, at the end of infusion, and as clinically indicated. In the event of hypersensitivity reaction, vital signs should be obtained at additional time points until recovery per investigator judgment.

6.3.7 12-Lead Electrocardiogram

Twelve-lead ECGs will be performed as indicated in [Table 14-1](#) under medical supervision. Before recording, subjects should be resting in a quiet supervised setting with minimal

stimulation (e.g., no television, loud music, and computer games) and lie in a resting position for 10 minutes before ECG recording.

All ECGs are to be read locally with local ECG equipment by an appropriately qualified and experienced ECG reader at the study site.

Corrected QT interval (QTc) value will be calculated using the Fridericia formula ($QTc = QT/(RR^{-1/3})$), QTc should be expressed in milliseconds, the provided formula assumes QT also in milliseconds and RR in seconds. The QTc interval will be automatically calculated. In the case of clinically significant ECG abnormalities, the investigator should report these as an AE if not due to a preexisting condition or if a preexisting condition worsens in frequency or intensity.

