9.6. Electrocardiogram

12-lead ECGs will be performed at screening, Week 12 (EOS/ET) and Week 26 visits and interpreted as “Normal”, “Abnormal, Not Clinically Significant” and “Abnormal, Clinically Significant”. A shift table comparing the interpretation at scheduled post-baseline visit with those at baseline will be presented by visit for the safety population.

A summary table with actual values and change from baseline will be presented for ECG parameters (ventricular rate, P-R interval, QRS duration, Q-T interval, QTcF) by scheduled visit.

The reference ranges for Ventricular rate: 60 - 100 beats/min; P-R interval: 120 – 200 msec; QRS duration: 80 – 120 msec; QTcF: \leq 450 msec. Based on the ranges the parameters will be interpreted as below.

- Abnormal Low
- Normal
- Abnormal High

All ECG data will be listed by visit for safety population.

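### Protocol 6.3.7 names the Fridericia correction but prints it with exponent -1/3 under a division, which would reverse the rate correction if the expression were applied as printed

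*Protocol*

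**What the plan says.** Protocol 6.3.7 (12-Lead Electrocardiogram) gives the only QTc formula in either document: "Corrected QT interval (QTc) value will be calculated using the Fridericia formula ($QTc = QT/(RR^{-1/3", where the quote stops just before the closing brackets. It fixes the units, saying that "the provided formula assumes QT also in milliseconds and RR in seconds". On how the value is obtained, it says "The QTc interval will be automatically calculated", without naming the device or system. It also says "All ECGs are to be read locally with local ECG equipment by an appropriately qualified and experienced ECG reader at the study site".

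SAP 9.6 prints no formula. It refers to QTcF by name and lists it with ventricular rate, P-R interval, QRS duration and Q-T interval. On reporting it says "A summary table with actual values and change from baseline will be presented for ECG parameters", by scheduled visit. It sets a reference range, "QTcF: \leq 450 msec" (that is, at most 450 ms), and adds "Based on the ranges the parameters will be interpreted as below", the classes being abnormal low, normal and abnormal high. The ECG visits are screening, Week 12 (EOS/ET) and Week 26.

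**The concern.** The name and the expression in the same sentence disagree. The measured QT interval shortens as the heart beats faster, so a rate correction has to raise QT at fast rates and lower it at slow ones. The expression as printed does the opposite: it shortens QT further at fast rates and lengthens it at slow ones.

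The formula stands in the methods text and comes with its units, so someone setting up an eCRF derivation or an analysis program could reasonably code it as it stands. At stake would be the QTcF rows of SAP Table 14.3.4.5.1 (actual value and change from baseline) and Table 14.3.4.5.3 (shift by parameter). High values at ordinary resting rates could be classed as normal, normal values at slow rates could be classed as high, and a change in heart rate between visits would show up as a false change in QTcF.

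**Working it through.** **Inputs.** The printed formula and units come from Protocol 6.3.7. The 450 ms limit comes from SAP 9.6, as does the range used to frame the size: "The reference ranges for Ventricular rate: 60 - 100 beats/min". The documents give no worked QTc value to reproduce. The QT values below, and the rate of 50 beats/min, are illustrative assumptions.

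**Algebra.** RR in seconds = 60 / heart rate.

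- As printed: QT / RR^(-1/3) = QT × RR^(1/3).
- Fridericia: QT / RR^(1/3) = QT × RR^(-1/3).
- Ratio, printed to Fridericia: RR^(1/3) × RR^(1/3) = RR^(2/3).

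The ratio depends on heart rate alone. It equals 1 only when RR = 1 s, which is 60 beats/min. Changing either the sign of the exponent or the division to a multiplication restores Fridericia.

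**Size for QT = 400 ms** (differences taken before rounding):

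| Rate (beats/min) | RR (s) | Fridericia (ms) | As printed (ms) | Difference (ms) | Ratio |
|---|---|---|---|---|---|
| 50 | 1.200 | 376.4 | 425.1 | +48.6 | 1.129 |
| 60 | 1.000 | 400.0 | 400.0 | 0.0 | 1.000 |
| 80 | 0.750 | 440.3 | 363.4 | -76.8 | 0.825 |
| 90 | 0.667 | 457.9 | 349.4 | -108.5 | 0.763 |
| 100 | 0.600 | 474.3 | 337.4 | -136.9 | 0.711 |

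Across the SAP's own ventricular-rate range of 60 to 100 beats/min, the printed form is therefore 0% to 29% too low (1 - 0.711 = 0.289).

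**Effect on the 450 ms class, if the printed form were used.**

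- QT 420 ms at 80 beats/min: 381.6 ms (normal) as printed, 462.3 ms (high) by Fridericia.
- QT 400 ms at 90 beats/min: 349.4 ms (normal) as printed, 457.9 ms (high) by Fridericia.
- QT 440 ms at 50 beats/min: 440 × 1.2^(1/3) = 467.6 ms (high) as printed, 440 / 1.2^(1/3) = 414.1 ms (normal) by Fridericia.

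The raw QT needed to exceed 450 ms shows the same thing:

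- At 80 beats/min: 450 × 0.75^(1/3) = 408.9 ms by Fridericia, 450 / 0.75^(1/3) = 495.3 ms as printed.
- At 100 beats/min: 379.5 ms by Fridericia, 533.5 ms as printed.
- At 50 beats/min the order reverses: 478.2 ms by Fridericia, 423.5 ms as printed.

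**Effect on change from baseline.** Take a subject whose Fridericia value is 400 ms at both visits, with a rate of 60 beats/min at the first and 80 at the second. The printed form gives 400 × 1 = 400 ms and then 400 × 0.825 = 330 ms, a false fall of about 70 ms produced by heart rate alone.

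**The case against.** The strongest reply is that nothing in the documents shows the printed expression being computed. The protocol names a standard method, has ECGs read locally and says the value is produced automatically. The SAP names QTcF, gives no derivation and does not list RR among its ECG parameters. If the devices apply Fridericia, the named method governs and the parenthesis is a slip on paper. This stands. A reader might infer that subjects will be misclassified against 450 ms; the documents support only that they would be if someone used the expression as it stands.

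The second reply is that the minus sign may not be in the protocol at all. The text was read from PDF by a program, and a superscript sign is easily distorted. This also stands, and it can be settled only by looking at the page.

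The third reply is that little depends on QTc. ECG is listed among the other safety endpoints in Protocol Table 2-1 and SAP 3.2 and is summarised descriptively. No eligibility criterion (Protocol 4.1) or withdrawal reason (Protocol 4.2.1) uses a QTc threshold. AE reporting of ECG findings (Protocol 6.3.2 and 6.3.7) does not refer to the 450 ms limit. The investigator's overall ECG interpretation is tabulated separately from the parameter ranges. This limits the consequence but does not make the formula right.

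Two further inferences should be resisted. One is a percentage of prolonged values missed: that needs distributions of heart rate and QTcF, which the documents do not give. The other is that sites' machines produce a mixture of corrections: the protocol prescribes Fridericia for all sites, and local equipment does not by itself imply otherwise.

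**Conclusion.** As the text reads, Protocol 6.3.7 is wrong: the expression is not the formula it names, and it reverses the direction of the rate correction. The proportional error follows from RR alone and needs no population assumption: none at 60 beats/min, 29% too low at 100 and 13% too high at 50. The examples in milliseconds rest on assumed QT values.

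The consequence is conditional on two things: that the minus sign is really on the page, and that some system or person uses the expression. Neither can be established from the documents. Even then, the effect would be confined to the QTcF rows of the descriptive ECG tables. Immunogenicity and the primary safety endpoints do not depend on it. This is a correction worth making because the formula is the only one given for a reported safety variable; it is not evidence that any reported value is wrong.

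**What to change.** 1. Check the exponent against the PDF page of Protocol 6.3.7. If there is no minus sign there, the formula needs no change.
2. If it is printed, correct it to QTcF = QT / RR^(1/3), with QT in ms and RR in s. A clarification letter would serve: the sponsor used one, dated 22 Jul 2020, to correct a missing date in the amendment heading.
3. Confirm that whatever calculates QTc automatically uses that form, and that the printed expression has not been coded in the eCRF or the analysis programs.

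The cost is one character in the protocol and one confirmation. As an optional check, QTcF can be re-derived from data the SAP already tabulates, using the Q-T interval and RR = 60 / ventricular rate, and compared with the recorded value. The correction does not depend on doing so.
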